The Sleep Apnea Management Clinic (SAM) is a novel group clinic created and embedded in the Cleveland Clinic (CC) System to address challenges in positive airway pressure (PAP) management by promoting adherence via providing access to problem-solving of PAP therapy issues. This innovative and interactive format allows patients with common problems and needs to have direct access to sleep medicine providers, sleep nurse practitioners, sleep nurses and/or durable medical equipment (DME) representatives all in one room in order to receive the most efficient service. While there are limited data focused on examining group clinics for PAP education, there are scant data that have assessed PAP adherence and its barriers in a group setting. Our team has played an integral role in the design, development, and establishment of the SAM Clinic initiative and has extensive experience in its management and operations. We propose a randomized controlled trial, involving 83 patients in SAM clinic and 83 patients in usual care and compare PAP adherence, patient reported outcomes and PAP barriers. Expected results will be of high impact given ability to identify and inform future treatment approaches for management of OSA with PAP and identify key outcomes for clinical trials. In doing so, this line of investigation will likely have a significant clinical impact to enhance PAP adherence and ameliorate adverse clinical outcomes associated with OSA patient populations across systems of care.

Specific Aims

SA 1. To examine the impact of the sleep apnea management (SAM) group-based intervention on Positive Airway Pressure (PAP) adherence (primary outcome) compared to a patient group managed by physicians (patients who follow usual care and are receptive to the SAM Clinic but do not participate in a SAM group) on changes from baseline to 1 and 3 months in those with moderate to severe OSA with suboptimal PAP adherence.

Hypothesis 1: We hypothesize that the SAM clinic intervention will result in improved PAP adherence versus usual care.

SA 2. To examine and compare changes in patient reported outcomes (PROs, i.e. daytime sleepiness, quality of life measures, and depressive symptoms) between the SAM Clinic and the usual care arms from baseline to 1 and 3 months in those with moderate to severe OSA with suboptimal PAP adherence. To examine the correlation between changes in PROs to changes in PAP adherence at each time point (secondary analyses).

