Eligibility criteria: Inclusion Criteria: 1) ≥18 years old 2) Moderate to severe OSA (apnea hypopnea index (AHI), respiratory disturbance index (RDI), Respiratory Event Index (REI)≥5 events/hr) on polysomnogram (PSG) or home sleep apnea testing (HSAT) 3) Followed by non-sleep and sleep providers for OSA 4) New PAP set up < 1 month 5) Sub-optimal PAP adherence by objective PAP adherence data (≤70 % usage and ≤4 hours of average PAP usage) Exclusion criteria: 1) Central sleep apnea (≥50% apneas are central) and/or presence of Cheyne-Stokes breathing 2) Pregnant women 3) Patients on supplemental oxygen 4) Patients not able to attend SAM clinic 5) Inability to provide informed consent

Randomization: Patients will be randomized 1:1 to SAM clinic/sleep hygiene or usual care/sleep hygiene (care by non-sleep providers) using a blocked randomization that stratifies patients based on OSA severity (AHI, RDI, REI 5-14.9, 15-29.9 vs. AHI, RDI, REI >30+). Random assignments to the three arms will be made

with the use of a randomization database in REDcap.

Study Protocol: All data from PAP devices set up by CCDME will be downloaded via wireless communication or smartcard. PAP adherence will be monitored by the research coordinator before randomization (randomized to SAM Clinic or usual care with their provider) and after 1 and 3 month of either intervention. A sample size of approximately 83 subjects is estimated in each group over a period of 2 years (total n=166). SAM clinic appointment will be offered within 1-2 weeks of patient consent and randomization into that group. Both groups will be provided with PAP barriers questionnaires which will be administered in "yes/no" format focused upon specific mask issues (air leak, irritation, fitting problems, type of mask) and other issues (nasal congestion, claustrophobia etc.) and the same questionnaires will be instituted in both the groups at the 1- and 3-month follow-up through the email using redcap platform. See Figure 2 for the flow diagram of the study.

[figure not shown]
[figure not shown]

Figure 2: Flow Diagram of Study

Sleep Hygiene Education: A research coordinator will provide both the arms with sleep hygiene education material at baseline that entails regularization of sleep wake schedule, stimulus control education, adequate amount of sleep and comfortable environment conducive to sleep (by mail).

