Data Analysis Plan: Patients will be randomized 1:1 to the two treatment groups using a blocked randomization that stratifies patients based on OSA severity (AHI, RDI, REI 5-15 vs.15-30, 30+). Blocks will be of random size blinded from study investigators. Only the intent-to-treat population will be included in primary analyses, while secondary analyses will be performed in the per-protocol population defined by participation in the SAM Clinic for the treated group versus usual care patients. Linear and non-linear mixed effect models will be used to compare groups for changes in PAP adherence (primary endpoint), PROs, and barriers over time. In these models, group by time interactions will be used to evaluate trend differences between groups, and mean differences primarily at 3 months and secondarily at 1 month. The use of mixed effect models will account for loss to follow-up under the assumption that such dropout is missing at random, though this assumption will be evaluated graphically. If data are missing not at random, pattern mixture models will be further explored to evaluate group differences. Analyses will be performed assuming an overall significance level of 0.05, and comparisons of mean differences at 1 and 3 months will each use a 0.05 significance level. Statistical support will be provided by a biostatistician within the Cleveland Clinic Department of Quantitative Health Sciences for this project.

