Sample Size: Sample size calculations were performed based on detecting mean differences in PAP adherence at 1 and 3 months. In this study, patients undergoing motivational enhancement (ME) showed an average PAP adherence of 264 minutes (SD: 174) as compared to average PAP adherence of 198 (SD: 168) among those without ME. Given the overall paucity of data addressing PAP adherence in a group setting-we utilized this data from RCT with ME given the similarities in approach. If we assume a similar effect size, and assume that average adherence will be log-normally distributed with a coefficient of variation of 0.65, there will be 80% power to detect an increase of 33% in the mean average nightly PAP adherence with 67 patients per group. Allowing for non-participation and non-compliance rates of 10% in each group, a total of 83 patients per group will be enrolled, the adjustment described by Lachin. This sample size will also provide similar power to detect moderate effect size differences between study groups on PROs, even allowing for dropout on these measures of up to 20% on these measures. Power calculations were performed using SAS software (version 9.4; Cary, NC) and assumed use of a two-sided test with significance levels of 0.05.

Limitations/Pitfalls and Alternative Strategies: Since this is a comparative study comparing the effectiveness of SAM clinic to usual standard of care by providers, there are inherent limitations to such a design. There is a possibility of cross over for the patients. We have accounted for possible cross-contamination in the statistical design by increasing the sample size. Patient without email access will be sent paper format of questionnaire. If recruitment become a challenge, will target recruitment efforts in primary care clinics. This study may not be able to shed the light on effectiveness specific mechanisms of SAM clinic intervention e.g. group component vs sleep provider interaction or more. Further research will be needed to investigate it.

Adverse Event Reporting: Reporting of adverse events will follow standard reporting guidelines. Each event will be classified according to its severity, whether it was expected or unexpected, and its likelihood of relatedness to the study and reviewed by the study medical monitor, [name].

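### 83 per group absorbs about 10% total dilution of the intent-to-treat contrast, which cannot cover both 10% non-compliance in each group and cross-contamination at 80% power

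*Combined protocol and SAP*

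**What the plan says.** The Sample Size section assumes log-normal nightly adherence with a coefficient of variation of 0.65 and takes its effect from 264 against 198 minutes, a 33% increase. On these inputs it gives 67 patients per group for 80% power; the calculation "assumed use of a two-sided test with significance levels of 0.05". It then inflates, citing a published adjustment without writing out the formula: "Allowing for non-participation and non-compliance rates of 10% in each group, a total of 83 patients per group will be enrolled".

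The Limitations/Pitfalls and Alternative Strategies section says "There is a possibility of cross over for the patients" and, shortly after, "We have accounted for possible cross-contamination in the statistical design by increasing the sample size". It gives no crossover rate, and no second increase in sample size is described anywhere.

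The Data Analysis Plan states "Only the intent-to-treat population will be included in primary analyses". A per-protocol comparison, which keeps SAM patients only if they took part in the clinic, is secondary. Specific Aim 1 describes the comparison group as "patients who follow usual care and are receptive to the SAM Clinic but do not participate in a SAM group".

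**The concern.** Under intent-to-treat, a SAM patient who never attends and a usual-care patient who does attend SAM both pull the arm means together, and the two effects add. An allowance for one is spent if the other uses it. The plan makes a single inflation, yet says that it covers a 10% rate in each of two arms and also contamination.

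Crossover is a real possibility here: the plan names it, and it describes the usual-care patients as open to the SAM Clinic. If dilution exceeds the allowance, a null intent-to-treat result could be read as coming from a trial with 80% power when it had less. The significance section also says that the data will supply effect sizes for multi-center trials, so readers need to know how much dilution the design can carry.

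**Working it through.** **Inputs (Sample Size and Data Analysis Plan).** Two-sided 0.05; 1:1 allocation; coefficient of variation 0.65; mean ratio 264/198 = 1.333; 67 per group before and 83 after inflation; intent-to-treat primary analysis.

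**Reproducing 67.** Log-scale SD σ = √ln(1 + 0.65²) = 0.594. Log effect δ = ln(1.333) = 0.2877. Normal approximation: n = 2(1.96 + 0.842)²σ²/δ² = 66.8, so 67. A t-test at 67 per group has 79.5% power. The plan's figure reproduces.

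**Reproducing 83.**
- Simple 10% loss: 67/0.9 = 74.4, so 75. No match.
- One 10% attenuation of the effect: 67/0.9² = 82.7, so 83. Match.
- Two successive 10% losses of patients: 67/(0.9 × 0.9) = 82.7, so 83. The same number with a different meaning.

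**Dilution model.** Let a be the proportion of SAM patients who do not attend, b the proportion of usual-care patients who attend SAM, and e the fraction of the SAM effect that those crossovers gain. Total dilution is D = a + e·b, and the intent-to-treat log effect is (1 − D)δ. The t-test noncentrality at n per group is (1 − D)δ/(σ√(2/n)). At n = 83 and D = 0 this is 0.2877/(0.594 × 0.1552) = 3.12.

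**Power, t-test.** With 10% of outcomes missing, n is 0.9 × 83 = 74.7 per group; that rate is an assumption.

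| Total dilution D | 83 per group, complete outcomes | 10% of outcomes missing |
|---|---|---|
| 0% | 87.4% | 84% |
| 5% | 83.9% | 80% |
| 10% | 79.8% | 75% |
| 15% | 75.1% | 71% |
| 20% | 69.9% | 65% |

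With complete outcomes, power falls to 80% at a D of about 10%: 9.7% by t-test and 10.3% by normal approximation. With a ratio of exactly 1.33, power is 86.8%, 79.1% and 69.2% at D = 0%, 10% and 20%. Simulation that mixes individual patients gives about 79% for 10% in one arm or 5% in each, and about 69% for 10% in each.

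**Possible meanings of 10% in each group.**
1. The usual-care 10% attend SAM. With a = b = 10%, full effect (e = 1) gives D = 20% and power of about 70%; half effect (e = 0.5) gives D = 15% and about 75%.
2. The usual-care 10% does not dilute the contrast, for example missed provider visits. Then a = 10% gives D = 10% and about 80%, and any crossover takes power below that.
3. Two successive patient losses. About 67 evaluable patients per group remain: 79.5% with no dilution and 70.7% at D = 10%.

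None of these keeps 80% power with both the stated rates and a margin for crossover.

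**The case against.** The strongest reply is that nothing is miscalculated: 67 and 83 both reproduce, and what remains is an undefined term. That is fair as to the numbers. But the definitions that fit the text all lead to the same result, so the ambiguity does not rescue the pair of statements.

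A reader might infer that the trial has only 70% power. The documents do not support that. The figure needs all of the usual-care 10% to attend SAM and gain its full effect. The Sample Size wording names non-participation and non-compliance, not crossover, and the per-protocol definition ties SAM participation to the treated arm. Other provisions limit dilution: usual-care patients are to follow up only with their own provider, patients unable to attend SAM are excluded, and the SAM visit is offered within 1–2 weeks. Late crossovers may gain only part of the effect by 3 months; with 10% SAM non-attendance and half-effect crossover in 5% of usual care, D = 12.5% and power is 77.5%.

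A mixed model that conditions on baseline adherence could also recover power. A baseline-outcome correlation of about 0.46 would restore 80% at D = 20%. The documents give no correlation and claim no such gain, and the eligibility cap on baseline use might lower it. In the other direction, complete outcomes are the favourable case. The Study Protocol section says "All data from PAP devices set up by CCDME will be downloaded via wireless communication or smartcard", but this does not guarantee completeness, and the Data Analysis Plan expects loss to follow-up.

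**Conclusion.** The point stands as an overstated allowance. On the plan's own inputs, 83 per group holds about 80% power only while total dilution, summed over both arms, is at or below about 10% and outcomes are complete. The plan claims more than that. In the assumed cases of 15% and 20% dilution, power is about 75% and 70%.

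Two further inferences go too far. The cross-contamination sentence is too broad, not wholly false: if SAM non-attendance is below 10%, the remainder can absorb some crossover. Nor do the documents establish that 83 is too few, since they give no crossover rate from which to resize.

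The result rests on the unadjusted log-scale comparison used for the plan's own calculation, and on non-attenders having the usual-care result. It does not depend on how the cited adjustment defines its rate, because power at 83 is computed directly. The threshold should be read as about 10%; the inputs do not support tenths of a percent.

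**What to change.** Keep 83 per group and the analysis. Make three wording changes.

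1. In Sample Size, write out the inflation formula and say which events the 10% covers in each arm: SAM non-attendance, usual-care attendance at SAM, missing outcomes, or something else.
2. Replace the power statement with:

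> Under the unadjusted log-scale comparison with complete outcomes, 83 per group gives about 87% power with no dilution, about 80% with a total dilution of about 10% summed over both arms, and, as assumed cases, about 75% at 15% and about 70% at 20%; if 10% of outcomes are also missing, power is about 84%, 75%, 71% and 65%.

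3. In Limitations, say that cross-contamination is covered only while total dilution from SAM non-attendance plus usual-care attendance at SAM stays at or below about 10%.

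The cost is wording only, with no extra patients. The downside is that the stated power becomes a less favourable, conditional range.
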